## **2.4 ANALYSIS TIMING**

The primary analysis will be performed at the end of the study, after the last patient has completed Week 36 final visit.

## **3. STUDY CONDUCT**

### **3.1 RANDOMIZATION**

After written informed consent has been obtained, all patients will receive a screening number assigned through the Interactive Voice and Web Response System (IxRS). After all patient eligibility requirements are confirmed on Day 1 visit the site personnel will contact the IxRS for assignment of a patient identification number (a separate number from the screening number).

Patients will be randomized in a 3:2:2:2:3 ratio to one of the study treatment arms A, B, C, D or E (see 2 for details):

Patients will be randomized on the same day the study treatment is to be initiated (Day 1 visit). After randomization and at each visit with study treatment administration (i.e., including Day 1) the IxRS will assign the appropriate study treatment kit to be used.

Randomization will be stratified for the two factors below:

- Baseline BCVA ETDRS letter score assessed on Day 1 (69 letters or better vs. 68 letters or worse)
- Presence/absence of retinal angiomatous proliferation (RAP) or polypoidal choroidal vasculopathy (PCV) at screening as assessed by the Reading Center

### **3.2 INTERNAL REVIEW COMMITTEE**

A Roche internal monitoring committee (IMC) will be responsible in the event of an interim analysis for sample size evaluation, operational/administrative purposes, and/or for safety data monitoring. For other objectives, the IMC will review the safety data and will be responsible for evaluating efficacy data for instance where assessment of benefit-risk is warranted. These analyses will take place at pre-defined time points or on an ad-hoc basis.

The IMC consists of a selected subset of Roche representatives including a biostatistician, safety representative, clinical science representative, clinical pharmacology representative, and pharmacometrician. The IMC members participating in a given interim analysis will be kept to the minimum required to address the objective of that interim analysis. Additional Roche Representatives might be involved to produce/process the unmasked listing/data to be analyzed by the IMC.

Full details regarding the IMC will be provided separately in the IMC agreement.

### **3.3 DATA MONITORING**

An IMC will review safety data, and may review efficacy data to assess benefit-risk.

## **4. STATISTICAL METHODS**

### **4.1 ANALYSIS POPULATIONS**

The following analysis populations will be defined: "Efficacy, Pharmacokinetic, and Pharmacodynamic Population" and safety population.

#### **4.1.1 Efficacy, Pharmacokinetic, and Pharmacodynamic Population**

All randomized patients will be included in the efficacy, PK, and PD analysis population. Patients who receive study drug in the study eye different than to which they were randomized will be included in the group to which they were randomized.

##### **4.1.1.1 Population A: All Patient Randomized to Arms A, B, C, and D**

Population A consists of all patients randomized to the treatment arms A, B, C and D. In this population, the baseline reference is the latest non-missing observation before start of study treatment. Population A will be used for the evaluation of efficacy in the treatment-naïve population.

##### **4.1.1.2 Population B: All Patients Randomized to Arms A and E**

Population B consists of all patients randomized to the treatment arms A and E. For this population, the Week 12 visit is the baseline for all efficacy and PD analyses. Therefore, the primary endpoint is BCVA change from Week 12. A subgroup of Population B, Population C, will be used for the evaluation of efficacy in the anti-VEGF-incomplete-responder population and is defined below.

#### **4.1.1.3 Population C: Anti-VEGF-Incomplete Responder Population**

The primary anti-VEGF-incomplete responder population is defined as sub-population of population B consisting of

- Population C: Patients in population B with BCVA  $\leq$  68 at Week 12 with at least one letter improvement relative to baseline.

Additional exploratory anti-VEGF-incomplete responder populations are defined as

- Population C1: Patients in population B with improvement of less than 15 letters at Week 12
- Population C2: Patients in population B without dry retina at Week 12 (dry retina definition No 2)

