3.2 RATIONALE FOR STUDY DESIGN

A multiple center, double-masked, randomized, comparator controlled trial design was selected to allow for an unbiased evaluation of RO6867461 as a treatment for patients with CNV secondary to AMD.

The study will allow evaluation of the efficacy of RO6867461 in treatment-naive patients (including 2 dose levels and 2 dose regimens) and patients who are switched to RO6867461 treatment after 3 administrations of ranibizumab. The latter group will allow for the assessment of RO6867461 in an anti-VEGF–incomplete-responder population using a predefined criterion based on a traditional secondary efficacy outcome in the target population (Sections 3.3.3.2 and 6.6.1.2):

- Patients with BCVA \leq 68 letters at Week 12

The double-masked design is achieved through the strict independence of the pharmacists (or designated personnel) and Investigators who are preparing and administering study treatment, from the assessing Investigators and remaining site personnel.

Sham administration will be delivered to patients in Arm D at Weeks 16, 24, and 32 to maintain double-masking throughout the study period.

To ensure the safety of all patients during the conduct of the study, several safety assessments have been included: e.g., regular ophthalmological monitoring (ocular safety panel and SD-OCT assessments), adverse events monitoring (systemic and ophthalmologic), vital signs (systolic blood pressure [SBP], diastolic blood pressure [DBP], and pulse rate), and laboratory safety tests.

Optional aqueous humor samples will be collected in consenting patients with an aim to further understand the ocular pharmacokinetics of RO6867461 and assess biomarkers (see Section 4.6.2). Single (Krohne et al. 2012) and multiple (Campochiaro et al. 2013) aqueous humor sampling has been instrumental in the understanding of ocular pharmacokinetics.

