6.6.1.2 Evaluation in the Anti-VEGF–Incomplete-Responder Population

For the evaluation of efficacy in anti-VEGF–incomplete-responder population, Population B and a subgroup of Population B will be used.

The subgroup is defined as:

- Patients with BCVA ≤ 68 Letters at Week 12

The study Week 12 visit will be considered the baseline for all efficacy evaluations for the anti-VEGF–incomplete-responder population.

The primary efficacy variable is BCVA change from Week 12 to Week 36. The primary efficacy analysis will be performed using a MMRM model. The model will include the categorical covariates of treatment group, visit, and visit by treatment group interaction, and the continuous covariate of Week 12 BCVA. Other covariates including the categorical stratification factors of baseline BCVA (≥ 69 letters vs. ≤ 68 letters) and

presence of RAP or PCV may also be incorporated as appropriate. An unstructured covariance structure will be used to account for within patient correlation, but another variance-covariance structure may be selected in case of convergence issues.

The primary statistical test will aim to test the null hypothesis (H_0) of no difference between the treatment group (Arm E) and the control group (Arm A), in terms of BCVA mean change from Week 12 to Week 36. The model-based estimate of the difference between the treatment group (Arm E) and the control group (Arm A) at Week 36, together with 95% Confidence and corresponding p-value will be reported as the primary efficacy measure in this population.

The mean and 95% CI within each treatment group and for the difference between RO6867461 treatment group and the control group at the other time-points will also be reported. There will be no formal correction for multiple testing.

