#### **4.4.2 Baseline**

For the evaluation in the treatment-naïve population, the baseline measurement is the latest non-missing observation before the first dose of study medication. For the evaluation in the anti-VEGF–incomplete-responder population, the baseline is the observation from Study Week 12. If the week 12 observation is missing, the patient will not be included in the incomplete responder population. For patients who did not receive any study medication, baseline will be set as the last available assessment before and including day 1.

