#### **4.5.1.2 Evaluation in the anti-VEGF Incomplete Responder Population C**

For the evaluation of efficacy in the anti-VEGF–incomplete-responder all patients in the population C will be used.

The primary efficacy variable is BCVA change from Week 12 to Week 36. The primary efficacy analysis will be performed using a MMRM model described in section 4.5.1.1.

The model-based estimate of the difference in change from baseline between the treatment group (Arm E) and the control group (Arm A) means at Week 36, together with 95% Confidence and corresponding p-value will be reported as the primary efficacy measure in this population.

The mean and 95% confidence intervals within each treatment group and for the difference between RO6867461 treatment group and the control group change from baseline at the other time points will also be reported. There will be no formal correction for multiple comparisons.

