#### **4.5.2 Secondary Efficacy Endpoints**

All analyses of secondary efficacy endpoints as defined in section 2.2.2 will be performed for population A and for population C, using their respective baseline definition (see 4.4.2).

For all secondary endpoints measured on a continuous scale, the same MMRM model used for the change from baseline BCVA will be employed. Nominal p-values for treatment effect will be reported for all post-baseline visits without correction for multiple testing.

Binary endpoints will be analyzed using Generalized Estimating Equations (GEE) with a binomial distribution, logit link function for odds ratios and identity link for risk differences, and unstructured covariance. In case of convergence issues, other covariance structures, such as AR(1) covariance structure, will be used.

The model will include the categorical covariates of treatment group, visit, and visit by treatment group interaction and randomization stratification indicator for presence of RAP or PCV and the continuous covariate of baseline outcome measure.

Least squares means on the probability scale for each treatment arm with the corresponding 95% confidence intervals and odds ratios relative to the control arm will be computed for all post-baseline visits.

Data transformation (e.g., logarithmic transformation) may be applied as appropriate. Other statistical models and additional analyses may also be performed as appropriate. Fisher's exact test may be used for binary endpoints in case GEE models do not converge.

In addition, the influence of baseline parameters will be evaluated as covariates in the MMRM model and in subgroup analysis as appropriate (see Section 4.5.5 ).

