## **STUDY DESIGN**

### **Description of Study**

Multiple-center, multiple-dose and regimen, randomized, active comparator controlled, double-masked, five parallel group, 36-week study in patients with CNV secondary to AMD. The five groups of this study are as follows:

- Arm A: 0.5 mg ranibizumab IVT every 4 weeks for 32 weeks (9 injections)
- Arm B: 1.5 mg RO6867461 IVT every 4 weeks for 32 weeks (9 injections)
- Arm C: 6 mg RO6867461 IVT every 4 weeks for 32 weeks (9 injections)
- Arm D: 6 mg RO6867461 IVT every 4 weeks up to Week 12 (4 injections), followed by 6 mg RO6867461 IVT every 8 weeks (i.e., on Weeks 20 and 28; 2 injections)
- Arm E: 0.5 mg ranibizumab IVT every 4 weeks up to Week 8 (3 injections), followed by 6 mg RO6867461 IVT every 4 weeks (6 injections)

The study will allow evaluation of RO6867461 in a treatment-naïve patient population (comparison of Arms A, B, C, and D) and an anti-VEGF–incomplete-responder patient population that meets a predefined criterion at Week 12 (comparison between Arms A and E). Only one eye will be chosen as the study eye.

---

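### The SAP's primary incomplete-responder population adds a one-letter-gain condition that the protocol lacks, without a usable reference visit, a stated reason or a restated sample-size basis

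*SAP*

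**What the plan says.** Protocol 3.2 says that the incomplete-responder population is identified "using a predefined criterion based on a traditional secondary efficacy outcome in the target population" and lists one item: BCVA of 68 letters or less at Week 12. Protocol 6.6.1.2 states that "Population B and a subgroup of Population B will be used" and defines the subgroup by the same 68-letter criterion alone. The synopsis reproduced in SAP Appendix 1 likewise refers to a population "that meets a predefined criterion at Week 12 (comparison between Arms A and E").

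SAP 4.1.1.3 names Population C as the primary incomplete-responder population and requires BCVA of no more than "68 at Week 12 with at least one letter improvement relative to baseline". It also lists two exploratory populations: C1 (gain of less than 15 letters at Week 12) and C2 (no dry retina at Week 12).

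On the meaning of baseline, SAP 4.1.1.2 says of Population B, the parent of C: "For this population, the Week 12 visit is the baseline for all efficacy and PD analyses". SAP 4.4.2 says that for the incomplete-responder evaluation "the baseline is the observation from Study Week 12".

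For the primary Arm E versus Arm A comparison, SAP 4.5.1.2 says that "all patients in the population C will be used". Secondary analyses (SAP 4.5.2) "will be performed for population A and for population C, using their respective baseline definition". Sensitivity analyses (4.5.4) and subgroup analyses (4.5.5) also name only A and C.

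SAP 2.3.2 gives 68 patients in each of Arms A and E, a 65% qualifying share, 10% drop-out, SD 9.7 letters, one-sided alpha 10%, approximately 80% power at 4.7 letters and a minimum detectable difference of 2.7. The protocol synopsis has the same numbers. Protocol 6.1.2 gives 4.8 and 2.8 for the same inputs, and adds a 50% share scenario (5.4 and 3.3 letters) that the SAP omits.

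**The concern.** Efficacy in incomplete responders is one of the two parts of the primary objective, and the two documents would answer it in different patients. Population C leaves out patients at 68 letters or less whose score at Week 12 was unchanged or lower than before treatment. The estimate therefore describes a different group from the one that the protocol specifies.

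Three practical consequences follow. The rule that selects a primary population points to the wrong visit if taken as written. The result for the protocol's own subgroup is not secured by the supplied SAP text. The qualifying share and power are carried over without saying whether they describe the protocol's subgroup or the narrower one. A favourable result in Population C could then be questioned as resting on an unexplained redefinition.

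**Working it through.** **1. The definitions side by side**

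| Source | 68 letters or less at Week 12 | Gain of at least 1 letter |
|---|---|---|
| Protocol 3.2 | yes | no |
| Protocol 6.6.1.2 | yes | no |
| SAP 4.1.1.3, Population C | yes | yes |

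Population C is nested in the protocol subgroup, so its share of Arms A and E can only be equal or smaller.

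**2. The reference visit.** With baseline set at Week 12, the change at Week 12 is Week 12 minus Week 12 = 0, which is never at least 1. C1, in the same list, uses a gain at Week 12 that only makes sense against the pre-treatment value. Day 1 is therefore the evident intention.

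**3. Coverage of the protocol subgroup.** C1 contains every patient whom Population C drops for not gaining, since a gain of zero or less is below 15 letters. But C1 also admits patients above 68 letters, and it leaves out patients at 68 or less who gained 15 or more. It is not the protocol subgroup.

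**4. Reproducing the stated power.** Inputs from SAP 2.3.2; two-sample normal approximation.

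- Completers per arm: n = 68 × 0.65 × 0.90 = 39.78
- SE = 9.7 × √(2/39.78) = 2.175
- Power at 4.7 letters = Φ(4.7/2.175 − 1.2816) = Φ(0.879) = 81.0% (noncentral t: 80.7%)
- Difference detectable with 80% power = (1.2816 + 0.8416) × 2.175 = 4.62 letters
- Minimum detectable difference = 1.2816 × 2.175 = 2.79 letters

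The approximately 80% is reproduced at the full 65% share. The recomputed 4.6 and 2.8 match neither printed pair exactly (4.7/2.7 and 4.8/2.8).

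**5. If only part of the protocol subgroup qualifies for Population C.** Let q be the proportion of patients at 68 letters or less who also gained a letter. The documents do not give q, so these values are assumptions. SD is held at 9.7, and n = 39.78 × q.

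| q | Share | n per arm | Power at 4.7 | Detectable with 80% power |
|---|---|---|---|---|
| 1.00 | 65.0% | 39.8 | 81.0% | 4.62 |
| 0.95 | 61.75% | 37.8 | 79.5% | 4.74 |
| 0.90 | 58.5% | 35.8 | 77.9% | 4.87 |
| 0.80 | 52.0% | 31.8 | 74.3% | 5.16 |
| 0.70 | 45.5% | 27.8 | 70.1% | 5.52 |

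Protocol 6.1.2's 50% scenario corresponds to q = 0.50/0.65 = 0.77. There n = 68 × 0.50 × 0.90 = 30.6 per arm, power at 4.7 letters is 73.0%, and the difference detectable with 80% power is 5.27 letters (the protocol prints 5.4).

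**6. Bias between arms.** Arms A and E both receive ranibizumab at Day 1, Week 4 and Week 8. Arm E first receives RO6867461 at Week 12, and the schedule of assessments places BCVA before dosing. Both parts of the selection rule are thus fixed before the treatments diverge.

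**The case against.** A SAP may refine a population, and requiring some gain fits the idea of an incomplete responder as opposed to a non-responder. That stands: nothing in the documents makes the protocol's definition the better one, and reverting to it is a preference. What is missing is the reason and the reconciliation.

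It can also be said that SAP 2.3 records how the sample size was originally set, so repeating its inputs is no error, and that 65% is a planning figure rather than a measured share. This also stands. A reader might infer that the stated 80% is wrong. The documents do not show that: q is unknown, at q = 0.95 the statement still holds, and a smaller SD in the narrower group could offset the loss (at q = 0.90, an SD of about 9.3 restores 80% at 4.7 letters).

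A reader might infer that Population C is empty and the primary analysis impossible. That is too literal. The intention is clear from C1, and the defect is one of wording.

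A reader might infer that the protocol's subgroup will go unanalysed. The supplied text does not establish this. SAP 4.5 defers to a List of Planned Outputs that was not available, 4.5.2 permits additional analyses, and C1 and C2 are also defined without being named in 4.5. What remains is that no supplied text commits to the analysis.

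**Conclusion.** The mismatch is in the text and should be fixed. One of the two primary comparisons is specified in two different populations, and the SAP's added condition names no usable reference visit.

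The effect on power is downward or nil if the 65% describes the 68-letter criterion and the SD is unchanged. Its size cannot be determined. The illustrative figures of 78% at q = 0.90 and 74% at q = 0.80 rest on assumed q, SD 9.7 and a simple two-sample comparison in place of the planned MMRM.

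A reader might also take the post-randomisation condition as biasing Arm E versus Arm A. The documents do not support this, because treatment up to the Week 12 assessment is the same in both arms. What changes is the group to which the estimate applies, and probably its precision.

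**What to change.** Before unmasking:

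1. Reconcile the definitions: either use the protocol's 68-letter criterion for Population C, or keep the narrower population and state the reason in SAP 4.1.1.3.
2. If the gain condition is kept, whether for the primary or for an exploratory population, write that the gain is relative to the Day 1 (pre-treatment) baseline.
3. If Population C stays primary, prespecify the same Arm E versus Arm A MMRM in patients with BCVA of 68 letters or less at Week 12 as a supportive analysis.
4. In SAP 2.3.2, say which definition the 65% and approximately 80% refer to, and carry over protocol 6.1.2's 50% scenario as the lower-share case.

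Minor: align 4.7/2.7 (SAP and synopsis) with 4.8/2.8 (protocol 6.1.2). Recomputation gives about 4.6 and 2.8, or 4.7 and 2.8 with completers rounded down to 39 per arm.

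The cost is mostly SAP wording, at most one extra analysis of data already collected, and possibly a slightly less favourable stated detectable difference. If the alignment is made in protocol 6.1.2 or its synopsis, that document changes too.

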#### **4.1.2 Safety Population**

All patients who have received at least one dose of the study treatment, whether prematurely withdrawn from the study or not, will be included in the safety analysis for this population. Patients who receive study drug in the study eye different from which they were randomized to will be included into the group to which their treatment profile match best.

### **4.2 ANALYSIS OF STUDY CONDUCT**

The number of patients who are enrolled, discontinued, and completed the study will be summarized as well as the major protocol violations. Demographic and baseline characteristics will be summarized with descriptive statistics. The analysis will be performed for populations A and C.

### **4.3 ANALYSIS OF TREATMENT GROUP COMPARABILITY**

Demographics, baseline characteristics (including ocular assessments, patient disposition, and medical history), and all baseline laboratory values will be summarized descriptively by treatment arm using frequency tables and summary statistics providing means, medians, standard deviations, first and third quartiles, and extreme values.

### **4.4 GENERAL CONSIDERATIONS**

#### **4.4.1 Visit Windows**

Visit windowing will be performed for this study with nominal visits/assessments falling outside of allowable protocol-defined visit windows, being reassigned to an appropriate visit for use in analyses.

If multiple valid (non-missing) values for a variable are recorded in the same visit window, one record will be selected for summary/analysis of the data by the following priority:

- The originally scheduled visit assessment

- The assessment closest to the target assessment day.

If scheduled assessments were grouped into multiple visits, the assessments will be assigned to a single visit provided all assessments fall within the same visit window.

Note that unscheduled visits could potentially be included in summaries and analyses following the application of these visit assignment rules.

Assessments that fall outside of the protocol-defined visit windows will be assigned to the closest target visit.

Unless otherwise specified, all analyses and summaries involving visit, will use visits assigned after visit windowing has been performed.

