3.1.1 Overview of Study Design

The five groups of this study (Figure 1) are as follows.

- Arm A: 0.5 mg ranibizumab IVT every 4 weeks for 32 weeks (9 injections)
- Arm B: 1.5 mg RO6867461 IVT every 4 weeks for 32 weeks (9 injections)
- Arm C: 6 mg RO6867461 IVT every 4 weeks for 32 weeks (9 injections)
- Arm D: 6 mg RO6867461 IVT every 4 weeks up to Week 12 (4 injections), followed by 6 mg RO6867461 IVT every 8 weeks (i.e., on Weeks 20 and 28; 2 injections)
- Arm E: 0.5 mg ranibizumab IVT every 4 weeks up to Week 8 (3 injections), followed by 6 mg RO6867461 IVT every 4 weeks (6 injections)

The study will allow evaluation of RO6867461 in a treatment-naive patient population (comparison of Arms A, B, C, and D) and an anti-VEGF–incomplete-responder patient population that meets a predefined criterion at Week 12 (comparison between Arms A and E). Only one eye will be chosen as the study eye.

Figure 1 Study Design

The total duration of the study for each patient will be up to 40 weeks, divided as follows:

- Screening: up to 4 weeks
- Baseline: Day 1
- Study Treatment Administration: from Day 1 to Week 32
- Final safety and efficacy period: from Week 32 to Week 36

Patients will be admitted to the investigational site on Day 1 and for subsequent scheduled visits, and will be discharged the same day after all mandatory and safety assessments as specified in Schedule of Assessments (SoA) are completed.

If a site has an unexpected issue (e.g., interactive voice and web response system [IxRS] is not able to assign the study kit, or the study treatment administration cannot be done on the same day due to unavailability of the unmasked investigators at the site), the patient's study treatment may be administered within 3 working days of the scheduled treatment visit with the Medical Monitor's permission.

The interval between two study treatment administrations needs to be at least 21 days.

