6.3.2.2 Population B: All Patients Randomized to Arms A and E

Population B consists of all patients randomized to the treatment arms A and E. In this population, the Week 12 visit is the reference for all efficacy and PD analyses. For example, the primary endpoint is BCVA change from Week 12. A subgroup of Population B will be used for the evaluation of efficacy in the anti-VEGF–incomplete-responder population.

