## **2.1 PROTOCOL SYNOPSIS**

The Protocol Synopsis is in Appendix 1. For additional details, see the Schedule of Assessments in [Appendix 2](#).

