Fundus Autofluorescence a	X					X							X	X	
SD-OCT a	X	X k	X	X	X	X	X	X	X	X	X	X	X	X	X
Fundus Fluorescein Angiography a	X					X							X	X	X
IndoCyanine Green Angiography a	X					X							X	X	X

Week	Screening	Week 1		Week 4	Week 8	Week 12	Week 13	Week 16	Week 20	Week 24	Week 28	Week 32	Week 36 Final Visit	Early Termination Visit	Unscheduled
		Day 1	Day 7	Day 28	Day 56	Day 84	Day 91	Day 112	Day 140	Day 168	Day 196	Day 224	Day 252		
Day	D-28 to D-1		+/-3	+/-3	+/-3	+/-3	-4/+3 m	+/-3	+/-3	+/-3	+/-3	+/-3	+/-3		
Visit Window														+7	
Assessments															
PK Sample a		X		X		X	X	X		X			X	X	X
PD Biomarkers Sample a		X		X		X	X	X		X			X	X	X
Exploratory Plasma Biomarker Sample a		X		X		X				X			X		
Aqueous Humor Sample (optional) a,d,i,g		X				X						X			X
Vitreous Humor + Blood Samples (optional) f,h												X			X
Clinical Genotyping Sample a,i,j		X													
Anti-Drug Antibody (ADA) a		X		X		X		X		X			X	X	X
Adverse Events a	X	X	X	X	X	X	X	X	X	X	X	X	X	X	X
Previous and Concomitant Treatments	X	X	X	X	X	X	X	X	X	X	X	X	X	X	X

- a Assessment prior to drug administration on days where study treatment is administered
- b Multiple assessments on a single visit day, details on timing on a separate table
- c Finger count vision assessment asap after, and within maximum of 15 min from study treatment administration
- d Assessment in study eye only
- e Performed prior to pupil dilation
- f Optional sample. Additional consent required from the patient
- g Unscheduled sample could be obtained at other or additional planned visits at the discretion of the Investigator in agreement with the participating patient
- h Only in case of vitrectomy surgery during the study and if vitreous sampling is feasible. A blood sample for plasma preparation should be drawn at the same time
- i Mandatory, except in countries where IRB/EC does not approve.
- j At Day 1 but can be done at any other visit if the sample not collected at baseline.
- k Baseline assessments
- l Assessment post-treatment administration in study eye only
- m Relative to the previous study treatment administration date (Week 12)

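### Does the nearest-visit rule in SAP 4.4.1 push late Week 12 BCVA values to Week 13 and drop those patients from Population C?

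*SAP*

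**What the plan says.** SAP 4.4.1 opens by saying that visits outside the protocol windows end up "being reassigned to an appropriate visit for use in analyses". Its working rule is: "Assessments that fall outside of the protocol-defined visit windows will be assigned to the closest target visit". Where one window holds several values of a variable, the originally scheduled assessment takes priority, then the one closest to the target assessment day. It adds: "Note that unscheduled visits could potentially be included in summaries and analyses following the application of these visit assignment rules".

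On the Population C baseline, SAP 4.4.2 states: "If the week 12 observation is missing, the patient will not be included in the incomplete responder population". Protocol 6.3.2.2 says of Population B: "In this population, the Week 12 visit is the reference for all efficacy and PD analyses".

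The schedules (Protocol Appendix 1, SAP Appendix 2) place Week 8 on Day 56, Week 12 on Day 84, Week 13 on Day 91 and Week 16 on Day 112. The BCVA row is blank at Week 13 in both. Scheduled BCVA carries footnote a: "Assessment prior to drug administration on days where study treatment is administered". Footnote m counts the Week 13 window from the Week 12 dosing date.

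The printed Week 12 window is +/-7 days in the protocol and +/-3 in the SAP's copy of the schedule. SAP 2.1 points to that copy: "For additional details, see the Schedule of Assessments in" its Appendix 2. Protocol 3.1.1 also sets a spacing rule: "The interval between two study treatment administrations needs to be at least 21 days".

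**The concern.** The Week 12 BCVA does two jobs for Population C: it decides who is in (68 letters or fewer, with at least one letter gained), and it is the baseline for the change to Week 36. A relabelled value therefore costs the whole patient, not one data point.

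Week 13 falls exactly on the last day of the protocol's Week 12 window. Any BCVA later than that is nearer to Day 91 or Day 112 than to Day 84. Followed word for word, the rule would never return a late value to Week 12, and patients with a valid pre-dose measurement would leave a primary analysis. The priority for the scheduled assessment does not help, because it applies only among several values in one window. The +/-3 window in the SAP's schedule looks as if it could widen the problem.

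**Working it through.** **Inputs.** Target days 56, 84, 91 and 112 and windows of +/-7 (Protocol Appendix 1); 68 patients per arm, 65% in the subgroup, 10% drop-out, SD 9.7, difference 4.7 letters, one-sided alpha 10% (SAP 2.3.2). The documents do not say how often Week 12 visits run late, so the losses below are assumptions.

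**1. The plan's own figure.** Evaluable patients per arm: 68 x 0.65 x 0.90 = 39.8. The standard error of the difference is 9.7 x sqrt(2/39.8) = 2.17 letters. Power for 4.7 letters is 80.7% by the noncentral t (81.0% by the normal approximation), which agrees with the stated figure of about 80%.

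**2. Which days are exposed.** Week 12 covers Days 77-91 and Week 16 covers Days 105-119, so a late Week 12 BCVA is out of window on Days 92-104, 13 days in all. The early side hardly matters. An in-window Week 8 dose is on Day 49 or later, and 49 + 21 = 70, so a Week 12 dosing visit cannot precede Day 70. Days 71-76 are nearest to Week 12, and Day 70 is a tie between Weeks 8 and 12.

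**3. Where Days 92-104 go.**

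| Reading | Week 12 | Week 13 | Week 16 |
|---|---|---|---|
| Literal, Week 13 fixed at Day 91 (midpoint with Day 112 is 101.5) | none | Days 92-101 | Days 102-104 |
| Literal, Week 13 at Week 12 dose + 7 days (footnote m) | none | Days 92-104 | none |
| BCVA visits only (56, 84, 112; midpoint 98) | Days 92-97 | none | Days 99-104 |

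Day 98 is a tie in the last row, and the SAP has no tie rule. Week 13 as a target is therefore the sole cause of loss for Days 92-97 only. Days 99-104 leave Week 12 even under the sensible mapping.

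**4. Which reading fits the section.** The first sentence asks for an appropriate visit. Duplicates are resolved variable by variable, by distance to the target assessment day. BCVA has no target day at Week 13. Under footnote m, Week 13 follows the Week 12 dose, so a BCVA taken before that dose cannot belong to it. In the treatment-naive analysis, the literal rule would also add a Week 13 level, filled only by late visits, to an unstructured model with nine scheduled BCVA visits (Weeks 4 to 36). A programmer would notice that.

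**5. The +/-3 copy.** If it were programmed, Days 88-91 would be out of window and nearest to Day 91. But 4.4.1 refers to protocol-defined windows, so +/-7 governs. With BCVA visits as the only targets, Days 88-91 stay at Week 12 under either window.

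**6. Size.** Two-sample noncentral t, SD 9.7, one-sided alpha 10%, starting from 40 per arm:

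| Lost per arm | Left per arm | Power for 4.7 letters | Difference detectable with 80% power |
|---|---|---|---|
| 0 | 40 | 80.9% | 4.63 |
| 1 | 39 | 80.1% | 4.69 |
| 2 (5%) | 38 | 79.4% | 4.75 |
| 4 (10%) | 36 | 77.7% | 4.88 |

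Population C also requires a gain of at least one letter, so 40 per arm is not shown to be its actual size. The relative loss does not depend on that number: the standard error grows by 1/sqrt(1 - f), which is 2.6% for f = 5% and 5.4% for f = 10%.

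**7. Bias.** Arms A and E both receive ranibizumab on Day 1 and at Weeks 4 and 8, and BCVA is measured before the Week 12 dose under masking. Lateness of that visit has no evident reason to differ by arm.

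**The case for a change.** The best case for a change is that the nearest-visit rule is the only operational instruction in 4.4.1, and the word appropriate is undefined. Two programmers could in principle produce different Population C memberships. Since Week 12 BCVA defines a primary population, its handling should not be left to discretion, and a few words would settle it.

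Part of this stands. The section does not say that targets are specific to the variable, it gives no rule for ties (Days 70 and 98), and the SAP's schedule prints a window that differs from protocol version 3. An unscheduled BCVA taken after the switch could also, in principle, stand in as the Week 12 value, but only if no scheduled value falls in that window, which is remote.

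The rest is weaker. The harmful reading requires assigning BCVA to a visit where BCVA is not measured. The further step, keeping every nominal Week 12 visit as Week 12 however late, is not clearly better. On Day 104 the baseline would be 20 days late and 8 days short of Week 16, and the planned 168-day interval to Week 36 (252 - 84) would shrink to 148 days (252 - 104). Excluding a patient with no value near Week 12 is a defensible rule, and it is set in advance.

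**Conclusion.** No change is needed. This is a gap that analysts fill sensibly: BCVA is mapped to visits where BCVA is scheduled, and the section's own wording supports that. What remains lost is Days 99-104, and possibly Day 98, which means patients seen 14 to 20 days after the target. Leaving them out is a fair trade-off.

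Even if the rule were followed literally, the result would be a small loss of precision with no evident bias. Power stays at 80.1% or 79.4% with one or two patients lost per arm, and falls to 77.7% with four. This rests on an assumed number of late visits, on the 40 per arm implied by SAP 2.3.2, and on lateness being unrelated to arm. The +/-3 against +/-7 mismatch is a clerical slip without effect here, because 4.4.1 uses the protocol's windows.
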